A Preliminary Study of Prophylactic Fentanyl Pectin Nasal Spray (FPNS) for Exercise-Induced Breakthrough Dyspnea

Principal investigator: [name]

Supportive Care Co-investigators: [name], [name], [name]

Biostatistics Co-investigator: [name]

Table of Contents

| | |
|---|----|
| A. Study Objectives | 2 |
| B. Background | 2 |
| C. Experimental Approach | 5 |
| D. Statistical Analysis | 11 |
| E. Data Confidentiality Procedures | 11 |
| F. References | 11 |

A. Study Objectives

Primary objective

To determine the effect of prophylactic fentanyl pectin nasal spray (FPNS) on the **intensity of exercise-induced breakthrough dyspnea** (numeric rating scale, adjusted for distance walked) between the **first** and **second** 6 minute walk tests. We aim to determine the effect size for both FPNS and placebo arm to inform a larger, adequately powered confirmatory randomized controlled trial.

Secondary objectives

1. To determine the effect of prophylactic FPNS on the **walk distance, neurocognitive function, and adverse effects** between the **first** and **second** 6 minute walk tests.
2. To determine the effect of prophylactic FPNS on the **intensity of dyspnea, walk distance, neurocognitive function, and adverse effects** between the **first** and **third** 6 minute walk tests.
3. To compare prophylactic FPNS and placebo on their ability to reduce the intensity of **exercise-induced breakthrough dyspnea, walk distance, neurocognitive function, and adverse effects** between the **first** and **second** 6 minute walk tests, and also between the **first** and **third** 6 minute walk tests.

B. Background

B.1. Significance of Dyspnea. Dyspnea is a subjective awareness of difficulty breathing, which may be associated with the distressing sensation of suffocation. It is one of the most common and most feared symptoms among cancer patients, occurring in up to 70% of patients in the last 6 weeks of life (Ben-Aharon et al. 2008). Dyspnea is associated with fatigue, anxiety, decreased function and quality of life, and increased mortality (Hauser et al. 2006, Maltoni et al. 2005).

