Although systemic opioids are established for management of dyspnea at rest, there are currently no evidence-based options for breakthrough dyspnea. In a case series, Bruera *et al.* reported the use of rescue morphine given subcutaneously for 312 episodes of breakthrough dyspnea in 45 cancer patients. After 30 minutes, 90% reported no to mild dyspnea (Bruera *et al.* 1993). Based on this study, most clinicians use a dose similar to the rescue opioid dose for breakthrough pain (i.e. 10-20% of total daily dose) to manage breakthrough dyspnea. However, a more recent double-blind randomized controlled trial comparing systemic fentanyl (oral or subcutaneous (SC)), nebulized fentanyl, and nebulized saline for breakthrough dyspnea found no significant difference in dyspnea relief at 10 minutes between the treatment arms (Charles *et al.* 2008). One of the reasons may be due to the short duration for the primary endpoint (10 minutes). To date, the evidence for opioid use for breakthrough dyspnea remains limited (Table 1). Further research is necessary to improve the management of this distressing and debilitating symptom.

Table 1. Studies of Opioids for Breakthrough Dyspnea

| Study | Methodology and patients | Agent and dose | Outcome |
|---|--|---|---|
| Bruera et al. Ann Intern Med 1993 (Bruera et al. 1993) | Prospective case series (45 cancer patients [pts]) | SC morphine 312 doses given (same dose as pain breakthrough) | After 30 minutes, 90% reported no-mild dyspnea; 5% mod-severe dyspnea |
| Benitez-Rosario et al. JPSM 2005 (Benitez-Rosario et al. 2005) | Retrospective case series (4 cancer pts) | OTFC 800mg/1200mcg 60mg/800mcg 120mg/600mcg 15mg/400mcg | RR decreased Dyspnea decreased by 90-100% in 20-60 minutes |

| | | | |
|---|---|---|---|
| Sitte et al. JPSM 2008 (Sitte and Bausewein 2008) | Retrospective case series (1 cancer pt, 2 heart failure pts) | Intranasal fentanyl 1/6 of MEDD | RR decreased, improved O ₂ saturation in all 3 patients Dyspnea scores not reported |
| Gauna et al. JPM 2008 (Gauna et al. 2008) | Prospective case series (2 COPD pts, 2 cancer pts) 10 episodes | OTFC 30mg/200mcg 720mg/400mcg 20mg/200mcg 24mg/200mcg | RR decreased Dyspnea decreased by 90- 100% in 20-60 minutes |
| Charles et al. JPSM 2008 (Charles et al. 2008) | Prospective, double blind crossover RCT (20 cancer pts) | Systemic hydromorphone Nebulized hydromorphone Nebulized saline | Dyspnea decreased similarly in all 3 arms (1.0, 0.9, 0.8) |

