C.1. Overall Study design. This is an investigator initiated study supported in part by Depomed, Inc. We propose a 2-arm, double blind, parallel randomized controlled trial of FPNS and placebo for cancer patients with breakthrough dyspnea (Figure 1). The main goal of this study is to determine the effect size for both FPNS and placebo arm to inform a larger, adequately powered confirmatory randomized controlled trial. After study consent, eligible patients will be asked to complete a number of surveys and a 6-minute walk test at baseline, rest until they return to baseline dyspnea, and then do a second 6-minute walk test 20 minutes after they have been given either FPNS or placebo prophylactically. They will then rest again to return to baseline dyspnea, and then do another 6-minute walk test 20 minutes after repeating the same dose of either FPNS or placebo (with at least 30 minutes between the first and second dose). This design will allow testing of both single and repeated dosing on dyspnea under a double blind design.

Based on our experience conducting symptom control trials, this study will take between 1.5-2 hours to complete on a single visit. We believe this study design is feasible and would not add undue burden for patients. Patients will be compensated with a \$50 gift card for their time and effort.

C.2. Eligibility Criteria. The eligibility criteria are shown in Table 2.

Table 2. Study Eligibility Criteria

[figure not shown]

Figure 1. Study Flow Chart

Inclusion Criteria

1. Diagnosis of cancer
2. Breakthrough dyspnea, defined in this study as dyspnea on exertion with an average intensity level $\geq 3/10$ on the numeric rating scale
3. Outpatient at MD Anderson Cancer Center seen by the Supportive Care Service or Thoracic Medical Oncology
4. Ambulatory and able to walk with or without walking aid
5. On strong opioids with morphine equivalent daily dose of 80-500 mg, with stable (i.e. +/- 30%) regular dose over the last 24 hours
6. Karnofsky performance status $\geq 50\%$
7. Age 18 or older
8. Able to complete study assessments

Exclusion Criteria

1. Dyspnea at rest $\geq 7/10$ at the time of enrollment
2. Supplemental oxygen requirement > 6 L per minute
3. Delirium (i.e. Memorial delirium rating scale > 13)
4. History of unstable angina or myocardial infarction 1 month prior to study enrollment
5. Resting heart rate > 120 at the time of study enrollment

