6. Systolic pressure > 180 mmHg or diastolic pressure > 100 mmHg at the time of study enrollment
7. History of active opioid abuse within the past 12 months
8. History of allergy to fentanyl
9. Unwilling to provide informed consent
10. Patients who currently have no evidence of disease

C.3. Study screening. A 2 step consent process will be used. First, a verbal consent will be obtained by the study staff to proceed with screening of potential participants for eligibility and to characterize their dyspnea using the dyspnea survey and the cancer dyspnea scale. Outpatients may be contacted by phone within 1 week prior to their scheduled clinic visit to informed them of this study so they can make necessary arrangements if interested in participating. Eligible patients will then be formally enrolled onto the study after they have signed the informed consent indicating a willingness for the patient to participate in the trial. The number of patients screened, approached, eligible and enrolled will be documented. Reasons for refusal for eligible patients will also be captured. Based on our experience with similar trials, we expect that a majority of patients will complete this study.

C.4. Randomization. A computer generated sequence in permuted blocks will be used to assign patients to either FPNS or placebo and provided via a secured website, stratified by baseline level of dyspnea NRS at rest at the time of enrollment (i.e. 0-3, 4-6). Biostatistics will set up a Randomization website. Investigational Pharmacy personnel will perform the randomization assignment.

C.5. Blinding. Both patients and the research staff conducting the assessment will be blinded to the treatment assignment. FPNS will be dispensed by Dispensing Pharmacy at MD Anderson. Placebo will be identical in appearance to the FPNS.

C.6. Research staff. An orientation will be held with research staff involved in this study to introduce them with the study design, and standardize the provision of each intervention.

C.7. Study Interventions. The supply of study medication (both FPNS and placebo) will be provided by Depomed, Inc. FPNS is FDA approved (NDA 022569/S-007) for treatment of breakthrough cancer pain in opioid-tolerant patients. Immediately upon patient enrollment, the study physician will be notified and will determine the morphine equivalent daily dose (MEDD) in real time using standardized equianalgesic ratios.

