Regulatory monitoring will be provided by the principal investigator, the Institutional Review Board (IRB), and the Data Safety and Monitoring Board (DSMB). Patient confidentiality will be ensured by use of study numbers, secure storage of clinical data, and anonymous reporting.

D. Statistical Analysis

D.1. Sample Size Calculation. Patients who have started the second walk test will be considered evaluable for this study's primary endpoint. 10 evaluable patients in the fentanyl arm provides 80% power to detect an effect size as small as 1.0 when alpha=5% using a two-sided paired t-test to compare dyspnea between the first and second walk tests. Results from this study will be used to calculate the sample size for an adequately powered randomized controlled trial.

D.2. Data Analysis. Summary descriptive statistics will be provided for demographics, outcomes, and other collected variables and will include proportions, medians, means, 95% confidence intervals, and other simple statistics as appropriate for the measure. Comparisons within arms will be performed using paired t-tests or signed rank tests.

E. Data Confidentiality Procedures

Health information will be protected and we will maintain the confidentiality of the data obtained from the patient's chart.

Collection of identifiers: We will collect and securely store patients' identifiers (including name, medical record number and demographic specifications). Each patient will be assigned a study number that will be the only identifier to figure in the analytical file and personal data will not be disclosed in any form. The key linking these numbers will be retained in a securely locked file by the investigator.

Data Storage: Protection of electronic and paper records will be guaranteed. All electronic records will be stored on password-protected institution computers behind the institution firewall. Any paper records will be classified and stored in locked files inside a locked office.

Training of personnel: Only MDACC personnel trained in maintaining confidentiality, the principle investigators and co-investigators, will have access to study records.

Data sharing: Study data will not be shared with any individuals or entities. The data will be kept by the principle investigator in a locked file cabinet.

Final disposition of study records: These data will be used only for this research study data files will be destroyed 5 years after publication of the findings.

F. References

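### D.2 states no between-arm contrast, so secondary Objective 3 (FPNS versus placebo) has no stated analysis, and the FPNS-arm change alone is not the effect of FPNS

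*Combined protocol and SAP*

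**What the plan says.** Section C.1 describes the design: "We propose a 2-arm, double blind, parallel randomized controlled trial of FPNS and placebo for cancer patients with breakthrough dyspnea". The primary objective in section A concerns the effect of FPNS on exertional dyspnea between the first and second walks, and adds "We aim to determine the effect size for both FPNS and placebo arm" as input to a later confirmatory trial. Secondary Objective 3 is a separate aim: "To compare prophylactic FPNS and placebo on their ability to reduce the intensity of" dyspnea, with walk distance, neurocognitive function and adverse effects also listed, for walks 1 to 2 and 1 to 3.

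D.1 sizes one arm for a two-sided 5% paired t-test of walk 1 against walk 2: "10 evaluable patients in the fentanyl arm provides 80% power to detect an effect size as small as 1.0". D.2 promises summary statistics, including means and 95% confidence intervals, and then one kind of comparison: "Comparisons within arms will be performed using paired t-tests or signed rank tests".

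On allocation, C.4 says "A computer generated sequence in permuted blocks will be used to assign patients to either FPNS or placebo", stratified by resting dyspnea (0-3, 4-6). The readable text gives no ratio and no placebo-arm size. Figure 1, the flow chart, is not shown in the text available for review and may give them.

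**The concern.** Objective 3 calls for a contrast between arms, and the plan names none. As written, it would be met by reading two separate before-after results side by side, and two separate results are not an estimate of their difference.

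The primary objective also treats the FPNS-arm change as the effect of FPNS. In that arm, drug is confounded with order: walk 1 always comes first and without study drug, and walk 2 always follows a dose. Placebo response, familiarity with the test, fatigue and regression to the mean all fall into the same before-after change. Only the randomised placebo arm can separate them from drug.

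What is at stake is interpretation and planning. A later placebo-controlled trial must be sized on the between-arm difference and its uncertainty, and this plan does not commit to reporting either.

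**Working it through.** **Step 1. The plan's own figure.** Inputs from D.1: n = 10, effect size d = 1.0 (in SDs of the paired change), two-sided alpha 5%, paired t-test. Degrees of freedom are 9, the critical value is 2.262 and the noncentrality is d√n = 1.0 × √10 = 3.162. Noncentral t power is 80.3%, and 80% power is reached at 0.996 SD. D.1 is reproduced.

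**Step 2. Is a between-arm contrast stated anywhere?**

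| Place | Content | Between-arm? |
|---|---|---|
| A, Objective 3 | FPNS versus placebo, walks 1-2 and 1-3 | Asked for |
| C.1, C.4, C.5 | Randomised, blinded, placebo-controlled | Design supports it |
| D.1 | Power for the FPNS arm, paired test | No |
| D.2 | Descriptive statistics with 95% intervals; paired or signed rank tests within arms | No |

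**Step 3. Can the FPNS-arm change be attributed to FPNS?** Its expectation is the drug effect plus the non-drug change, and the paired test responds to the sum. The documents bear on the non-drug part as follows.

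- C.11 lets only patients whose dyspnea rose at walk 1 go on. Selection on a high first reading favours a later fall.
- C.10 lets patients be dosed for the next walk once dyspnea is within 1 point above baseline. Residual dyspnea could push the other way.
- Table 1 reports similar dyspnea falls in all three arms of an earlier crossover trial (1.0, 0.9, 0.8), nebulized saline included. The setting differs, so this shows the risk without sizing it.

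The documents therefore give neither a size nor a net direction. As an illustration only, take no drug effect and an assumed non-drug change of 0, 0.25, 0.5 or 1.0 SD. The n = 10 paired test is then significant with probability 5.0%, 10.9%, 29.3% or 80.3%. A between-arm test stays at 5% in each case, because a shift common to both arms cancels.

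**Step 4. Precision of the missing contrast.** Assumptions not in the readable text: placebo-arm size, equal SDs and normal changes. For a two-sample t-test on change, the standard error in SD units is √(1/n₁ + 1/n₂).

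- 10 versus 10: standard error √0.2 = 0.447, 18 df, critical value 2.101. The half-width is 2.101 × 0.447 = 0.94 SD. At 1.0 SD the noncentrality is 1/0.447 = 2.236 and power is 56.2%. Power of 80% is reached at 1.32 SD.
- 10 versus 5, to show the effect of a smaller placebo arm (nothing in the text suggests this size): standard error √0.3 = 0.548, 13 df, critical value 2.160. The half-width is 1.18 SD, power at 1.0 SD is 39.4%, and 80% is reached at 1.66 SD.

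**Step 5. What ANCOVA would add.** Adjusting for the walk-1 value multiplies the variance of change by (1 + r)/2, where r is the walk 1-walk 2 correlation, and the two covariates cost 2 df. The documents give no r. For 10 versus 10 and assumed r of 0.5 and 0.7, the formula puts 80% power at 1.16 and 1.23 SD. Simulation that allows for chance walk-1 imbalance gives about 1.19 and 1.27 SD, which are the safer figures. Near r = 0.85 the gain over a simple difference in change has gone: both have about 56% power at 1.0 SD.

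**The case against.** The strongest defence is that this is a preliminary study whose stated main goal is an effect size in each arm. D.2 gives descriptive statistics with 95% intervals for outcomes, and the arms are independent. If mean changes and their intervals are reported by arm, a reader can derive the difference and its interval. This reduces the harm but does not remove it: D.2 does not say that its intervals are for change, nor that any is for a difference, and Objective 3 is a written objective in its own right. Low between-arm power is acceptable here; the gap is the missing analysis.

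A reader might infer several stronger things that the documents do not support.

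- **That the sample size is wrong.** It is correct for the within-arm test it names.
- **That the placebo data go unused.** D.2 plans paired comparisons in both arms, and per-arm effect sizes are an aim. Only the contrast between arms is absent.
- **That the plan carries a 29% or 80% false-positive rate.** Those figures rest on assumed shifts, and the plan has no efficacy decision rule.
- **That the bias is known to favour FPNS.** C.10 and C.11 can pull in opposite directions.
- **That the placebo-arm size is missing from the protocol.** Figure 1 may give it.

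The between-arm contrast has a limit of its own. Dosing precedes walk 2 by 20 minutes, and under C.11 and D.1 patients who have not started walk 2 are not evaluable and are replaced. Someone stopped after dosing but before walking would leave the comparison, so the evaluable set is not fully protected by randomisation.

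**Conclusion.** The point holds and should be fixed. No between-arm estimate is stated for Objective 3, and the FPNS-arm change from walk 1 to walk 2 cannot by itself be read as the effect of FPNS. The finding about the text does not depend on any assumption. The size of the non-drug change is unknown, so no bias can be quantified.

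The between-arm precision in Step 4 depends on the assumed placebo-arm size. With 10 per arm, the effect detectable with 80% power is about 1.32 SD, against the 1.0 SD that D.1 gives for the within-arm change. The harm falls on interpretation and on planning the next trial; no pre-set efficacy decision is affected.

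**What to change.** **In D.2**

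- Add the between-arm difference in NRS dyspnea change, walks 1 to 2 and 1 to 3, with 95% confidence intervals, labelled as estimation and not powered. ANCOVA on arm, the walk-1 value and the resting-dyspnea stratum is preferable; a difference in mean change is the acceptable minimum. Use the same NRS outcome definition as the within-arm analysis.
- Report matching differences for walk distance and neurocognitive scores.
- Summarise adverse-effect ratings by arm without a walk-1 covariate, because Table 4 schedules none before dosing.
- Base statements about the effect of FPNS on the between-arm estimate, and keep the paired results as within-arm description.
- Report by arm the patients who were dosed but not evaluable.

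**In D.1**

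- Say that the 80% power is for the within-arm change only.
- Unless Figure 1 already gives the placebo-arm size, state it together with the between-arm precision.

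**Cost.** Plan wording and some extra models on data already scheduled. Dyspnea, distance and the five neurocognitive measures in Table 4, note 11, make 7 outcomes; at 2 walk contrasts each, that is 14 estimates. No new patients or assessments are needed. The downside is a visibly wide interval and a less favourable detectable effect on paper.
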